4.2 Treatment Groups

Treatment groups in the DBT Phase are rimegepant 75 mg EOD/placebo EOD, rimegepant 75 mg daily (i.e., quaque dia [QD]), and placebo QD. The safety analysis sets are assessed by astreated treatment group (i.e., actual treatment received), the randomized, full, efficacy, and migraine analysis sets are assessed by as-randomized treatment group, and the enrolled analysis set is assessed overall.

If a subject takes ≥ 1 dose of planned randomized DB study drug, then that subject is considered to have as-treated treatment group equal to as-randomized treatment group (see Section 6.2.6.2).

If there are non-randomized subjects who take study drug, then the as-randomized treatment group of "not randomized" is included in the full analysis set augmented with the safety analysis set.

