9.2 Analysis Sets

The following analysis sets will be used in this study:

- Enrolled: Subjects who sign informed consent and are assigned a subject identification number
- Full: Subjects in the enrolled analysis set who receive a randomized treatment group assignment (rimegepant or placebo)
- Double-blind treatment safety: Subjects in the enrolled analysis set who take ≥ 1 dose of double-blind study drug (rimegepant or placebo)
- Open-label rimegepant safety: Subjects in the enrolled analysis set who take ≥ 1 dose of open-label rimegepant
- Double-blind or open-label rimegepant safety: Subjects in the enrolled analysis set who take
 ≥ 1 dose of double-blind or open-label rimegepant
- Double-blind treatment efficacy: Subjects in the full analysis set who are randomized only
 once, and take ≥ 1 dose of double-blind study drug
- Migraine: Subjects in the double-blind treatment efficacy analysis set with ≥ 14 days of eDiary efficacy data (not necessarily consecutive) in both the Observation Phase and ≥ 1 month (4-week interval) in the Double-blind Treatment Phase

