4 ANALYSIS SETS, TREATMENT GROUPS, AND SUBGROUPS

4.1 Analysis Sets

The following analysis sets are evaluated and used for presentation and analysis of the data:

• Enrolled: Subjects who sign an informed consent form and are assigned a subject identification number, i.e., nonmissing informed consent date. This analysis set is used mainly to assess study population and in by-subject listings.

- Full: subjects in the enrolled analysis set who receive a randomized treatment assignment from the IWRS, i.e., nonmissing IWRS randomization date. This analysis set is used mainly to assess study population.
- Safety: subjects in the enrolled analysis set who take ≥ 1 dose of study drug (DB rimegepant, OL rimegepant, or placebo), i.e., nonmissing study drug start date. This analysis set is used to assess study population and produce select by-subject listings.
 - OBT safety: subjects in the safety analysis set who take ≥ 1 dose of DB study drug (rimegepant or placebo), i.e., nonmissing DB study drug start date. This analysis set is used to assess study population, exposure, and on-DBT safety.
 - OL rimegepant safety: subjects in the safety analysis set who take ≥ 1 dose of OL rimegepant, i.e., nonmissing OL rimegepant start date. This analysis set is used to assess study population, exposure, and on-OL rimegepant safety.
 - Interim safety: subjects in the OL rimegepant safety analysis set with OL rimegepant start date DB study drug last date > 7 days. This analysis set is used to assess post-DBT pre-OL rimegepant safety.
 - Ouble-blind (DB) or OL rimegepant safety: subjects in the safety analysis set who take ≥ 1 dose of DB or OL rimegepant, i.e., nonmissing DB or OL rimegepant start date. This analysis set is used to assess study population, exposure, and on-DB or OL rimegepant safety.
 - o Follow-up safety: subjects in the safety analysis set whose last contact date is in the follow-up safety analysis period. This analysis set is used to assess follow-up safety.
- DBT efficacy: subjects in the full analysis set who are randomized only once and take ≥ 1 dose of DB study drug (rimegepant or placebo). This analysis set is used to analyze outcomes research during the DBT Phase.

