- Cumulative DB or OL rimegepant exposure (mg), derived by summing {number of days × number of tablets taken per day × dose} across records with complete study medication start date and kit type identifier of DB rimegepant EOD/placebo EOD, DB rimegepant QD, or OL rimegant.
 - o If the kit type identifier is DB rimegepant EOD/placebo EOD, then the dose is 37.5 mg.
 - o If the kit type identifier is DB rimegepant QD or OL rimegepant, then the dose is 75 mg.
- Average DB or OL rimegepant exposure (mg per day), derived as cumulative DB or OL rimegepant exposure/time on DB or OL rimegepant (days)
- Total DB or OL rimegepant exposure (tablets) summed across all subjects, derived by summing cumulative DB exposure across all subjects
- Total DB or OL rimegepant exposure (patient-years), derived by summing (DB or OL rimegepant end date DB or OL rimegepant start date + 1)/365.25 across all subjects.

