 - Subjects randomized to placebo QD placebo who took (1) ≥ 1 tablet from a DB rimegepant QD or DB rimegepant EOD/placebo EOD wallet, and (2) no tablets from a DB placebo QD wallet.
 - At least once. Defined as any of the following:
 - Subjects randomized to rimegpant EOD/placebo EOD who took ≥ 1 tablet from a DB rimegepant QD or DB placebo QD wallet

- Subjects randomized to rimegepant QD who took ≥ 1 tablet from a DB rimegepant EOD/placebo EOD or DB placebo QD wallet
- Subjects randomized to placebo QD who took ≥ 1 tablet from a DB rimegepant QD or DB rimegepant EOD/placebo EOD wallet.
- Time on DB study drug > 14 weeks.

Results for all categories are displayed, even those with 0 counts.

OL Rimegepant Treatment Compliance

The frequency table of OL rimegepant treatment compliance is provided by treatment group and overall for the OL rimegepant safety analysis set, and displays the following categories:

- OL rimegepant tablet count compliance ≥ 80% from OL rimegepant start to later of last scheduled OLE Phase visit or OL rimegepant end. Tablet count compliance is derived as 100 × actual cumulative OL rimegepant tablet count/required cumulative OL rimegepant tablet count, where
 - Actual cumulative OL rimegepant tablet count is derived by summing the {number of days × number of tablets taken per day} across records with complete study medication start date and valid OL wallet ID.
 - Required cumulative OL rimegepant tablet count is derived as {OL maxdate OL rimegepant start date + 1} where
 - OL maxdate is defined as the latest of the (1) scheduled Week 14, 16, 20, and 24/EOT visit dates, and (2) OL rimegepant end date. Scheduled visits are identified from visit labels, and therefore exclude those containing "unscheduled" in the visit label.
- > 1 OL rimegepant tablet taken on any 1 day. This is determined from either of the following:
 - Records with complete study medication start date, valid OL wallet ID, and number of tablets taken per day > 1
 - Overlapping records with valid OL wallet ID (see Section 9.4)
- Time on OL rimegepant > 14 weeks
- OL rimegepant start on or before DB study drug end. Defined as nonmissing OL rimegepant start date ≤ DB study drug end date.
- OL rimegepant taken but DB study drug never taken. Defined as nonmissing OL rimegepant start date and missing DB study drug start date.

Results for all categories are displayed, even those with 0 counts.

eDiary Usage Compliance

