- OL rimegepant start date: earliest complete study medication start date from IP Dosing CRF records with number of tablets taken per day > 0 and valid OL wallet ID. This is an analysis period reference date.
- OL rimegepant end date: latest of (1) complete study medication start dates, or (2) complete study medication end dates from IP Dosing CRF records with number of tablets taken per day > 0 and valid OL wallet ID
- OL rimegepant last date:
 - Before the LSLV database lock: OL rimegepant end date derived only for subjects with "yes" or "no" response to the phase completion question on the OLE Subject Status or Follow-up Subject Status CRF
 - LSLV database lock: OL rimegepant end date

This is an analysis period reference date.

• DB or OL rimegepant start date: study drug start date for subjects whose as-treated DB treatment group is rimegepant EOD/placebo EOD or rimegepant QD; OL rimegepant start date for subjects whose as-treated DB treatment group is placebo QD. This is an analysis period reference date.

- DB or OL rimegepant end date: study drug end date for subjects whose as-treated DB treatment group is rimegepant EOD/placebo EOD or rimegepant QD; OL rimegepant end date for subjects whose as-treated DB treatment group is placebo QD
- DB or OL rimegepant last dose date: study drug last date for subjects whose as-treated DB treatment group is rimegepant EOD/placebo EOD or rimegepant QD; OL rimegepant last date for subjects whose as-treated DB treatment group is placebo QD. This is an analysis period reference date.
- OP start date: earliest of the following: screening visit date 1 day; eDiary efficacy data date. The screening visit date is determined from the visit label from the Visit Date CRF. This is an analysis period reference date.
- OP end date:
 - If the study drug start date is nonmissing: study drug start date − 1 day
 - \circ If the study drug start date is missing and the randomization date is nonmissing: randomization date -1 day
 - If both study drug start date and randomization date are missing: last contact date
 This is an analysis period reference date.
- Last contact date:
 - Earliest complete death date from the AE CRF, if it exists.

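### The start-date test for the pooled rimegepant safety set leaves out placebo-randomised subjects who took tablets from both placebo and rimegepant wallets and never took open-label rimegepant

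*SAP*

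**What the plan says.** Protocol 9.2 defines the pooled set by dosing alone: subjects who take "≥ 1 dose of double-blind or open-label rimegepant". SAP 4.1 keeps that wording and adds an operational test: "subjects in the safety analysis set who take ≥ 1 dose of DB or OL rimegepant, i.e., nonmissing DB or OL rimegepant start date".

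Three other rules decide what that test does:

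- SAP 4.2: after at least one dose of the planned randomised double-blind drug, "that subject is considered to have as-treated treatment group equal to as-randomized treatment group".
- SAP 7.1: the DB or OL rimegepant start date is the "study drug start date for subjects whose as-treated DB treatment group is rimegepant EOD/placebo EOD or rimegepant QD", but the "OL rimegepant start date for subjects whose as-treated DB treatment group is placebo QD". The end and last dates follow the same split.
- SAP 6.2.6.1: cumulative DB or OL exposure in mg is summed over records by wallet, using the "kit type identifier of DB rimegepant EOD/placebo EOD, DB rimegepant QD, or OL" rimegepant. The as-treated group plays no part. Average exposure divides this sum by time on DB or OL rimegepant, which runs between the dates in SAP 7.1.

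The SAP foresees the situation. SAP 6.2.6.2 tabulates, under incorrect drug taken at least once, placebo-randomised subjects with one or more tablets from a rimegepant wallet ("1 tablet from a DB rimegepant QD or DB rimegepant EOD/placebo EOD wallet"). Only the separate all-the-time category, which requires that no placebo-wallet tablet was taken, moves a subject to another as-treated group. Table 4 in SAP 6.1.1.1 also has a column for placebo subjects who never take open-label rimegepant.

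**The concern.** The start-date test stands in for a dosing fact, but it is computed from a group label that a single correct tablet fixes. Where the label is placebo and a double-blind rimegepant wallet was also used, the test can answer no although rimegepant was taken.

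The pooled set carries real output:

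- SAP 6.4.1.5: AEs by worst intensity, SAEs and exposure-adjusted AEs.
- SAP 6.4.2.2: LFT elevations, exposure-adjusted LFT elevations and time to first elevation.
- SAP 6.4.6: every narrative identifier except death.
- SAP Table 3: the pooled set is named in the summary for exploratory objective 8.

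A subject wrongly outside the set contributes neither events nor exposure to these outputs. A non-fatal SAE or a marked liver elevation in that subject does not trigger a narrative through this listing. For extension entrants the stake is different: the double-blind rimegepant period is missing, and the exposure average is internally inconsistent.

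**Working it through.** The plan states no figure on this point, so there is nothing to reproduce. The check applies SAP 4.1, 4.2, 6.2.6.2 and 7.1 to the four possible patterns of a placebo-randomised subject who took at least one tablet from a double-blind rimegepant wallet.

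| Placebo-wallet tablet? | OL rimegepant? | As-treated group | DB or OL rimegepant start date | At least 1 dose? | In set by start date? |
|---|---|---|---|---|---|
| No | No | Rimegepant | Study drug start | Yes | Yes |
| No | Yes | Rimegepant | Study drug start | Yes | Yes |
| Yes | No | Placebo | Missing | Yes | **No** |
| Yes | Yes | Placebo | OL start | Yes | Yes, from OL start only |

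One pattern of the four contradicts the definition. The fourth satisfies it but loses the double-blind rimegepant period. SAP 6.4.1.5 starts the exposure-adjusted period at this date, and SAP 6.4.2.2 counts time to first elevation from it.

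**Average exposure in the fourth pattern.** The formula is 75 mg × (double-blind rimegepant QD tablets + OL tablets) / OL days, with one tablet a day. The tablet counts are illustrative.

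- One 8-tablet wallet and 80 OL days: (8 × 75 + 80 × 75)/80 = (600 + 6,000)/80 = 82.5 mg/day.
- 8 tablets and 84 OL days: 6,900/84 = 82.1 mg/day.
- 28 tablets and 84 OL days: 8,400/84 = 100 mg/day.
- 56 tablets and 84 OL days: 10,500/84 = 125 mg/day.

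One 75 mg tablet a day cannot average more than 75 mg/day. If the first example counts the 8 double-blind days in the denominator as well, 6,600/88 = 75 mg/day. The excess comes entirely from numerator and denominator covering different days.

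**Number of subjects.** The documents give no dispensing-error rate, so no count can be derived. For scale only, 84 days / 8 tablets = 10.5, or about 11 wallets per subject; 11 × 220 = 2,420 wallets in the placebo arm. An assumed 0.1% wallet error gives about 2.4 errors. If an assumed 10% to 30% of those subjects take no OL rimegepant, about 0.2 to 0.7 subjects are left out. Neither rate has a source in the documents.

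**The case against.** The strongest reply is that the gap is narrow and the subject is not lost. Much of that stands.

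- *Narrow.* A reader might infer that any placebo-randomised subject given a rimegepant wallet falls out of the set. The rules do not say so. A subject who took only rimegepant wallets is reassigned and kept, and one who takes OL rimegepant is kept. IWRS assigns specific container numbers (SAP 2.2), so errors should be few.
- *Objectives 7 and 8.* A reader might infer that the hepatic secondary results are compromised by this exclusion. Their summaries in SAP Table 2 use the DBT and OL rimegepant safety sets, so membership of the pooled set does not alter them. SAP 6.4.2.2 does list pooled LFT tables among the output supporting objective 7, but the specified summary is elsewhere. That an event on a mis-dispensed wallet sits in the placebo column of the DBT tables follows from the as-treated rule itself, a separate convention that this point leaves in place.
- *Events hidden.* A reader might infer that such events disappear. They remain in the DBT safety tables, the enrolled-set AE and LFT listings (SAP 6.4.1, 6.4.2), the safety-set LFT line plots with dosing days (6.4.2.2), the study drug listing with wallet ID and kit type (6.2.6.1), and the compliance and deviation output (6.2.6.2, 9.1).
- *Core SAP.* Safety analysis periods and further narrative details are deferred to a document not available here, so some downstream effects cannot be fully confirmed. The set definition and the dates, however, are written in this SAP.

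None of this makes the start-date test equivalent to taking at least one dose, or makes an average above 75 mg/day possible.

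**Conclusion.** Wrong as written; low impact. Applied literally, SAP 4.2 and 7.1 make the test in SAP 4.1 contradict its own definition, and that of Protocol 9.2, for one dosing pattern that combines two situations the SAP itself provides for. For mixed-wallet subjects who enter the extension, the set is right but the period is truncated, and average exposure mixes mg from one span with time from another.

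The effect is confined to descriptive, untested safety output in the pooled set and to the non-fatal narrative identifiers. Efficacy is analysed as randomised and is untouched. The conclusion rests on the rules as printed in this SAP and assumes that the Core SAP does not override the dates in SAP 7.1.

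**What to change.** In SAP 4.1 and 7.1, base membership and the DB or OL rimegepant start date on the first tablet from a wallet whose kit type is DB rimegepant EOD/placebo EOD, DB rimegepant QD or OL rimegepant, whatever the as-treated group. State that any tablet from an EOD wallet counts as rimegepant by convention, since those wallets alternate active and placebo tablets. SAP 6.2.6.1 already credits such tablets with 37.5 mg each.

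For mixed-wallet subjects, derive time on rimegepant and the on-rimegepant period from the rimegepant-kit wallet intervals, each with the SAP's 7-day extension for events. Do not use a single first-to-last span. Suppose one QD wallet is taken on days 8 to 15, placebo on days 16 to 84 and OL rimegepant on days 85 to 168. The single span is 168 − 8 + 1 = 161 days, of which 84 − 16 + 1 = 69 are placebo. The intervals give 8 + 84 = 92 days, and 92 × 75 / 92 = 75 mg/day, so mg and time cover the same days.

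Keep the as-treated columns in the DBT tables, and footnote placebo-column events that start after a first rimegepant-wallet tablet.

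The cost is SAP wording and a revised date and interval derivation. Wallet ID, dosing dates and kit type are already merged for exposure, so no new data are needed.

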4.3 Subgroups

Subgroup tables present results by subgroup level and overall for subjects with nonmissing subgroup level data.

The following efficacy subgroups are of interest for the migraine analysis set:

• Randomization stratum – use of previous prophylactic migraine medication generally considered to have efficacy: yes, no (see Section 6.2.5.4).

Randomization strata are based on the actual data, not those assigned by IWRS.

Medical history of hypertension is a safety subgroup of interest for hypertension-related safety endpoints for the DBT and OL rimegepant safety analysis sets (see Section 6.2.5.3). Refer to the Core SAP for the subgroup definition.

5 SAMPLE SIZE, POWER, AND TYPE 1 ERROR

The study randomizes approximately 220 subjects per arm. Based on data from study C4951025 (BHV3000-305), we estimate that this results in roughly 200 subjects per arm in the migraine analysis set. Assuming rimegepant provides roughly a 1.1-day advantage over placebo on the primary endpoint, a common standard deviation (SD) of 3.5 days, and a 2-sided alpha level of 0.025, then the study has roughly 80% power on the primary endpoint.

In study C4951025 (BHV3000-305), rimegepant provided a 0.8-day advantage over placebo. With daily dosing, we expect the treatment effect to increase. Using the data from study BHV3000-305, the SD of the primary endpoint was estimated to be roughly 3.5 days.

Type 1 error is controlled using a 2-sided alpha level of 0.025 and hierarchical testing. The significance of the primary endpoint is evaluated at a 2-sided alpha level of 0.025 for each rimegepant dosing regimen versus placebo. If the primary endpoint is significant for a rimegepant dosing regimen, then the secondary efficacy and outcomes research endpoints are tested hierarchically, each at a 2-sided alpha level of 0.025, in the order specified in Section

3.2.2. Thus, for a rimegepant dosing regimen, a secondary efficacy or outcomes research endpoint is tested only if the preceding secondary endpoint in the hierarchy is determined to be significant (i.e., p-value ≤ 0.025). If a test in the hierarchy is not significant, then any further tests on endpoints in the sequence have p-values presented only for descriptive purposes, and no conclusions are drawn from those results. Note that secondary safety endpoints are not tested.

For exploratory endpoints, no attempt is made to adjust for multiplicity. Any exploratory endpoints for which p-values are produced are evaluated at an unadjusted, 2-sided alpha level of 0.025 and presented only for descriptive purposes.

6 STATISTICAL ANALYSES

All statistical analyses are performed using SAS statistical software (Version 9.4 or higher).

6.1 General

6.1.1 Programmed Output

A list of TLFs and corresponding templates are presented separately in a mock TLF document corresponding to this SAP.

Refer to the Core SAP for additional details about programmed output.

6.1.1.1 Tables

Treatment Group Presentation

Treatment group presentation in tables by analysis set is shown in

Table 4. Exceptions are specified in subsequent sections as needed.

Table 4 Treatment Group Presentation in Tables by Analysis Set

| Analysis Set | Number of Columns | Abbreviated Treatment Group |
|---|-------------------|---|
| Enrolled | 1 | Overall |
| Full, DBT efficacy, migraine, safety, DBT safety, interim safety by treatment group and {overall} | 3 to 4 | RMG EOD/PBO EOD RMG OD |
| | | PBO QD {Overall} |
| OL rimegepant safety, DB or OL rimegepant safety by treatment group/OL rimegepant and overall | 4 | DB RMG EOD/PBO EOD/OL RMG DB RMG QD/OL RMG DB PBO QD/OL RMG Overall |

| Number of Columns | Abbreviated Treatment Group |
|--------------------------|-----------------------------|
| 6 | DB RMG EOD/PBO EOD/OL RMG |
| | DB RMG QD/OL RMG |
| | DB PBO QD |
| | DB PBO QD to OL RMG |
| | DB PBO QD No OL RMG |
| | Overall |
| | |

"DB PBO QD to OL RMG" denotes as-treated DB placebo QD subjects in the OL rimegepant safety analysis set, and "DB PBO QD No OL RMG" denotes as-treated DB placebo QD subjects not in the OL rimegepant safety analysis set; note that these 2 placebo groups add to the "DB PBO QD" group.

Results for study population and pretreatment safety endpoints also include overall treatment group (see Sections 6.2 and 6.4).

6.1.1.2 Figures

Refer to the Core SAP for additional details.

6.1.1.3 Listings

Unless otherwise specified, by-subject listings are sorted by randomization status (randomized, not randomized), site-subject ID, and additional variables such as time points, as applicable. Listings display as-randomized treatment group abbreviated as (1) "RMG/PBO", "RMG", and "PBO" for subjects in the full analysis set, and (2) "NRND" for subjects not in the full analysis set.

Listings of significant protocol deviations, exposure, safety parameters, outcomes research parameters include the following: abbreviated name of the analysis period in which the measurement was slotted (i.e., PRETRT, DBT, INT, OLRMG, FU; this does not apply to exposure parameters); analysis visit in which the measurement was slotted (this does not apply to exposure or AEs); measurement date/time; study day derived from the measurement date, and rimegepant study day ≥ 1 derived from the measurement date for as-randomized placebo QD subjects (see Section 7.3).

6.1.2 Statistical Methods

Refer to the Core SAP for descriptive statistics in tables, counting rules in frequency tables, and rounding rules in frequency tables.

6.1.3 Missing Data

All analyses are based on observed data unless otherwise specified. See Section 6.3 for statistical methods for handling missing data in efficacy analyses.

